Using a stepped-wedge cluster randomized trial (RCT), we will evaluate the effects of this stepped care depression model, the protocol of which this paper describes in detail. The primary objective of the study is to assess whether the integrated depression care model is superior to usual care on (1) reducing depression symptoms and functional impairment (primary outcomes); (2) improving physical health for those with HIV, diabetes and/or hypertension (secondary outcomes); and (3) reducing perceived mental health stigma and increasing retention in IC3 care (care processes). We will also evaluate the incremental cost-effectiveness of integrating evidence-based depression care, relative to usual care, and track mental health-related outcomes among household members of patients. If efficacious and cost-effective, this study will provide a model for integrating depression care into HIV clinics in Malawi, and the study will promote social wellbeing among household members.

METHODS

Study Design

This is a prospective, stepped-wedge cluster randomized trial to evaluate the effects of an evidence-based depression care model, relative to usual care, on mental and physical health outcomes of patients seeking care at integrated chronic care centers (IC3) in Neno, Malawi. The study will take place at fourteen health clinics in Neno District, which will constitute our clusters. Clinics will be randomized to one of five arms, each comprising 2-3 health clinics, such that the clinics receive the intervention in a random order and all clinics receive the intervention by the end of the study (Figure 1).

Figure 1. Stepped wedge design of IC3D clinical trial

Period	Period 1			Period 2			Period 3			Period 4			Period 5			Period 6			Period 7			Period 8			Period 9			Period 10		
Month	1	2	3	4	5	6	7	8	9	10	11	12	13	14	15	16	17	18	19	20	21	22	23	24	25	26	27	28	29	30
Arm 1	Pre	Pre	Pre	Int	Int	Int	Post	Post	Post	Post	Post	Post	Post	Post	Post	Post	Post	Post	Post	Post	Post	Post	Post	Post	Post	Post	Post	Post	Post	Post
Arm 2	Pre	Pre	Pre	Pre	Pre	Pre	Int	Int	Int	Post	Post	Post	Post	Post	Post	Post	Post	Post	Post	Post	Post	Post	Post	Post	Post	Post	Post	Post	Post	Post
Arm 3	Pre	Pre	Pre	Pre	Pre	Pre	Pre	Pre	Pre	Int	Int	Int	Post	Post	Post	Post	Post	Post	Post	Post	Post	Post	Post	Post	Post	Post	Post	Post	Post	Post
Arm 4	Pre	Pre	Pre	Pre	Pre	Pre	Pre	Pre	Pre	Pre	Pre	Pre	Int	Int	Int	Post	Post	Post	Post	Post	Post	Post	Post	Post	Post	Post	Post	Post	Post	Post

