The Integrated Chronic Care Clinics Depression (IC3D) module draws from best evidence on collaborative care models for depression in low-resource settings.^{40,41} We will use a gold standard, stepped-care approach to offering psychological and pharmacologic treatment across all treatment facilities and clinics. Usual care will be augmented with evidence-based Problem Management Plus (PM+) through provision of manualized, group-based counseling sessions, and antidepressant therapy (ADT) for those with severe depression (or if PM+ is

declined), which is consistent with WHO mhGAP guidelines⁴² for use of ADT. The primary components of the depression care model are described below.

Psychoeducation and treatment selection: If eligible for treatment, the counsellor will inform the client of the availability of PM+ and ADT as treatment options, in addition to encouraging the client to access general supports—such as peer support groups—within Neno. Psychoeducation on depression, treatment course, possible side effects, and benefits of treatment will be provided. Clients will have the autonomy to select their preferred treatment, but the counsellor will encourage clients with moderate depression (PHQ-9 < 15) to consider group-based PM+ counseling given its established efficacy and absence of significant side effect concerns, while adults with moderate-to-severe and severe depression (PHQ-9 ≥ 15) will be encouraged to consider joint ADT and group-based PM+. If the client remains depressed after 12 weeks of receiving either depression treatment modality (as measured by PHQ-9 at quarterly visits), s/he will be offered to switch to or add the other form of treatment.

In the event an enrolled individual no longer meets criteria at treatment initiation, the individual will leave the cohort and not be eligible for treatment but will continue to be evaluated every three months for future eligibility. Given that screening, diagnosis and enrollment will occur at all facilities over the full trial period, we expect any reduction in patients enrolled in the cohort due to lagged treatment initiation will be offset by newly-identified individuals over this same period. This is consistent with an open cohort design for stepped-wedge trials.⁴³

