Provider experience: In Year 5, we will interview up to 10 providers including clinical officers who prescribed ADT, as well as psychosocial counsellors who led PM+ sessions. In addition to discussing perceived strengths and weakness of the intervention and its implementation, we will also discuss the training and supervision process, as well as provider job satisfaction and burnout.

Patient experience: A random sample of 20 participants (10 male, 10 female) will be interviewed after their final study assessment to assess their experiences with the intervention – including logistical aspect of participation, impact on personal mental health and wellbeing, as well as changes in relationships at the household level.

Sample Size

We assumed $n=30$ enrollees per facility (total $n=420$) during each three month “step”, based on an estimated 10% depression prevalence in Malawi.^{7,84} We further assumed loss to follow-up of 15%, based on intervention trials we have conducted in similar settings.^{11,85}

The power calculation is based on the model described in the analysis section (see below) and a two-sided null value of no effect.⁸⁶ To indicate the precision of the study design, we report “minimum detectable effect” sizes across the range of our primary outcomes at 80%

power, with a type I error rate of 0.05, and conservative intraclass correlation coefficient (ICC) of 0.05, a cluster autocorrelation coefficient (CAC) of 0.80, and an individual autocorrelation coefficient (IAC) 0.80. Table 2 reports these effect sizes.

Analysis of Intervention Effects

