The data from the trial will be analyzed using a generalized linear mixed model framework, which is standard for stepped-wedge cluster designs.^{87,88} The patients participating form an open cohort with repeated measures, as it will be possible to link each patient taking a PHQ-9 screening and any subsequent exams over time. The models will be at the patient-level, nested within clinic-months and clinics. The primary outcomes are: (i) prevalence of depression; (ii) depression severity (PHQ-9 score) conditional on having depression; (iii) WHODAS score conditional on having depression; and (iv) utility score (0 to 1) from the EQ-5D-5L. The first outcome is a dichotomous event for if the patient has depression or not, while the remaining outcomes are treated as continuous. For the principal analysis of the trial, we used the “complete” stepped-wedge of data from months 1 to 18; long-term follow-up will constitute a secondary analysis.

We specify the following model for patient $i = 1, \dots, N$ in clinic $j = 1, \dots, J$ at time period $t = 1, \dots, T$:

$$y_{ijt} \sim F(g(\eta_{ijt}))$$

$$\eta_{ijt} = \mu + x'_{ijt}\beta + z'_{jt}\gamma + \delta D_{(i)jt} + \theta_i + \alpha_j + \phi_{jt} + \tau_t$$

where y_{ijt} is the outcome, $F(\cdot)$ is an appropriate likelihood and $g(\cdot)$ is a suitable link function, x_{ijt} and z_{jt} are respectively patient and clinic level covariates, τ_t are monthly fixed effects, and $\theta_i \sim N(0, \sigma_\theta^2)$, $\alpha_j \sim N(0, \sigma_\alpha^2)$, and $\phi_{jt} \sim N(0, \sigma_\phi^2)$ patient-, clinic-, and clinic-time random

effects term. We will take both intention to treat (ITT) and per protocol approaches. For the ITT analysis, the variable D_{jt} is an indicator equal to one if cluster j is in the intervention state at time t and zero otherwise, thus δ represents our estimated treatment effect. For per protocol analysis D_{ijt} will be a patient-level variable equal to one if the clinic was in the intervention state and the patient completed the treatment as defined above, and zero otherwise. For dichotomous outcomes, we will use a Bernoulli distribution with logistic link function, for continuous outcomes a normal distribution with identity link function. The same models will be used for secondary outcomes.

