The parameters of interest are δ_k , which are a (log) odds-ratio for the prevalence outcome and a mean absolute difference in score for the three individual-level outcomes. We will take both intention to treat (ITT) and per protocol approaches for the individual level outcomes. For the ITT analysis, the variable D_{jt} is an indicator equal to one if cluster j is in the intervention state at time t and zero otherwise. Thus, δ represents our estimated treatment effect. For the per protocol analysis, D_{ijt} will be a patient-level variable equal to one if the clinic was in the intervention state and the patient completed the treatment as defined above, and zero otherwise. As we describe below, we will use a randomisation test method to derive exact inferential statistics (p-values and confidence intervals) for the parameters of interest.

Outcomes 2-4 described above are only recorded for those who screen positive for depression at their scheduled visit. Thus, the data do not all cover the full patient population: data for outcomes 2 to 4 are a subset of those for outcome 1. Based on this, we anticipate the data to be normally distributed. However, we will test this assumption by examining QQ plots and conducting KS (Kolmogorov Smirnov) and SW (Shapiro Wilk) tests. In the event the normality assumption is violated, we will consider an alternative specification, such as a two-part semi-continuous model.

Statistical Inference

All models will be estimated separately using restricted maximum likelihood, using the R package lme4. We will report point estimates, confidence intervals, and p-values but not make any claims of "statistical significance", given recent strong arguments against doing so [2].

P-values will be based on the null hypotheses $H_0: \delta_k = 0$ versus the two-sided alternatives $H_1: \delta_k \neq 0$ in each of the models defined above. Given that there are multiple primary outcomes, we will adjust reported p-values for multiple testing using a cluster-based stepdown method, which provides an efficient means of controlling the family-wise error rate [18]. The full methodology is described elsewhere, but we describe it here briefly.

Let there be P hypotheses to be tested H_1, \dots, H_P with associated test statistics T_p . We let the ordered test statistics be:

$$T_{[1]} \geq T_{[2]} \geq \dots \geq T_{[P]}$$

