The implementation outcomes are divided into three categories:

1. Screening:
 - a. Proportion of patients screened with the PHQ-2, out of those attending IC3 clinics.
 - b. Proportion screening positive with PHQ-2, out of those who were administered the PHQ-2.
 - c. Proportion screened on the PHQ-9, out of those who screened positive on the PHQ-2.
 - d. Proportion screening positive on PHQ-9, out of those who were administered the PHQ-2.
2. Diagnosis:
 - a. Proportion of patients who are administered the BDIS, out of those who screened positive on the PHQ-9.
 - b. Proportion of patients who receive a diagnosis using BDIS, out of those administered the BDIS.
3. Treatment:
 - a. Proportion of patients attending treatment sessions (PM+, ADT, both), out of those who have been enrolled in the IC3D clinical trial and elected to receive treatment (PM+, ADT, both)
4. Protocol Fidelity:
 - a. Proportion of reviewed mastercards appropriately completed by clinical officers
 - b. Proportion of patient registration forms appropriately completed by counsellors
 - c. Proportion of PM+ components appropriately covered within each PM+ therapy session

Each step is a potential point of failure that could limit the acceptability or effectiveness of the intervention. Analysis of the implementation outcomes constitutes a descriptive analysis intended to support interpretation of trial results.

We will report the overall trial mean proportions of each implementation outcome along with 95% confidence intervals. Note that the screening and diagnosis outcomes are available for both treatment and control conditions, while the treatment outcomes are only available in treatment units. We will also examine the temporal changes in the implementation outcomes by reporting within each three-month block mean proportions and associated uncertainty intervals.

Secondary analyses

In addition to the usual issues of adherence, such as patients refusing treatment or not attending scheduled treatment, we have identified that patients diagnosed in one month or trial “block” may not be treated until the subsequent month or trial block. At an individual level, non-adherence would

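### In the primary ITT analysis of outcomes 2-4, scores from a patient's admitting screen, taken before any care, count as intervention outcomes once the clinic has switched

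*Protocol*

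**What the plan says.** - **Entry.** Protocol, Study Design: attendees are screened at every time point, and those who screen positive join the cohort and are followed to the end of the study.
- **When entry happens.** Protocol, Treatment: IC3D, places it throughout the trial: "Given that screening, diagnosis and enrollment will occur at all facilities over the full trial period". Protocol Table 1 marks eligibility screening and consent in two quarters only. It also lists a baseline assessment separately from follow-up.
- **When care is offered.** Protocol, Study Participants and Treatment: IC3D: PHQ-9 first, then the diagnostic interview, then discussion of treatment options with those eligible.
- **What is analysed.** Protocol, Analysis of Intervention Effects: "it will be possible to link each patient taking a PHQ-9 screening and any subsequent exams over time". SAP, Statistical model: "Outcomes 2-4 described above are only recorded for those who screen positive for depression at their scheduled visit".
- **Exposure.** In the ITT analysis of both documents, D is a clinic-by-time indicator, identical for every patient in the clinic.
- **Lag.** The SAP addendum accepts that "patients diagnosed in one month or trial “block” may not be treated until the subsequent month or trial block". It adds a CACE as a secondary analysis. Both documents also plan a per-protocol analysis with a patient-level D.
- **Period effects.** The protocol model has time fixed effects. The SAP equations display none, although their cluster-level covariates are not named.

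Neither analysis text excludes the entry score or says how the baseline assessment is used, and the patient-level covariates are not named.

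**The concern.** The positive screen that admits a patient also supplies the first value of the severity outcome, with WHODAS and EQ-5D recorded at that visit. For a patient who enters after the clinic has switched, these values describe someone not yet treated, but the ITT model reads them as results of the intervention. This recurs for each new entrant, however long ago the clinic switched, so modelling time since switch-over would not remove it.

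Three of the four primary outcomes are affected. With period effects in the model, the estimate depends partly on how many new cases screening finds, not only on how well care works. Without them, a second problem arises: patients are selected at PHQ-9 ≥ 10, so entry scores tend to be high, and they are over-represented in early periods, when most clinics are still controls.

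**Working it through.** **Plan's own figure.** Protocol, Sample Size, assumes 30 per facility and 420 in total per step: 14 × 30 = 420, which reproduces. The minimum detectable effects are in Table 2, which is not in the text available, so they could not be checked.

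**Inputs from the protocol.** 14 clinics in five arms of 2-3 (taken as 3, 3, 3, 3, 2); months 1-18, so six quarters, with one arm switching per quarter from quarter 2; ICC 0.05, CAC 0.80, IAC 0.80; 15% loss; two-sided 5% test, 80% power.

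**Variance components (total 1).** Clinic 0.05 × 0.80 = 0.04; clinic-period 0.05 − 0.04 = 0.01; patient 0.95 × 0.80 = 0.76; residual 0.95 − 0.76 = 0.19.

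**Assumptions.** The true effect is 0 at the entry visit and Δ at every later visit in a switched clinic. All later visits are scored. Loss is 3% per step (0.97⁵ = 0.859, about 14% over five steps).

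**Method.** Expected GLS estimate from the protocol model: period fixed effects, with clinic, clinic-period and patient random effects.

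**Share of entry records in the D=1 data.** Switched clinic-quarters: 3×5 + 3×4 + 3×3 + 3×2 + 2×1 = 44.
- *30 new patients per clinic per step, then followed:* 44 × 30 = 1,320 entry records among about 5,790 D=1 records, or 23%.
- *Entry in Table 1's two quarters only* (15 per clinic in each, assumed): only Arm 1 is switched in quarter 2, giving 3 × 15 = 45 entry records among about 1,210, or 4%.

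**Results with period effects.** The MDE is the true Δ, in SD units, needed for 80% power: SE × (1.960 + 0.842) ÷ share of Δ retained.

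| Pattern | Retained, all records | MDE, all records | MDE, entry visits excluded in both states |
|---|---|---|---|
| Table 1 entry, two quarters | 90% | 0.161 | 0.157 |
| 30 new per clinic per step | 70% | 0.175 | 0.134 |
| Steady pool, 10% entry (assumed) | 91% | 0.155 | 0.155 |
| Steady pool, 20% entry (assumed) | 83% | 0.173 | 0.164 |
| Steady pool, 33% entry (assumed) | 74% | 0.203 | 0.180 |

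The steady pool holds 30 records per clinic per step, with the stated share newly entered at each step. Excluding entry visits in both states returns 100% of Δ in every row.

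**Power.** For a true effect equal to the undiluted MDE, power is Φ(retained × 2.802 − 1.960). At 90% retained this is Φ(0.56) = 71%. At 70% it is Φ(0.00) = 50%.

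**Results without period effects.** The estimate keeps about 100% (Table 1 pattern) or 97% (30 new per step). If entry scores exceed later ones by h through selection, the estimate moves in favour of the intervention by 0.54h and 0.66h respectively. With period effects this shift is close to zero.

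**Excluding entry visits only in switched clinics** is not valid: it favours the intervention by 0.07h (Table 1 pattern) and 0.29h (30 new per step).

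**The case against.** **The target may be the clinic population.** SAP, Analysis of Primary Outcomes, speaks of severity among those with depression in this patient group, and the addendum puts real-world ITT effects first. On that reading, cases found but not yet treated belong with D=1. This stands as a reason to keep the all-records model in the report. But neither document defines such an estimand, and prevalence already carries a clinic-level effect. ITT requires keeping patients whatever care they receive; it does not require counting a measurement made before care was offered.

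**The plan has seen the lag.** A reader might infer that the authors overlooked delayed or absent treatment. They did not: the CACE and per-protocol analyses address it. Both are additional, and the per-protocol definition does not say how visits before treatment is completed are coded.

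**The size may be modest.** A reader might infer that the estimate is simply one minus the entry share, or that entry records form half or more of the data. Neither is supported. In a followed open cohort the entry share changes over time, and the simple rule misses in both directions: at 33% it gives 67% against 74% here, and at 23% with steady inflow 77% against 70%. The 30 per facility per step may be cluster-period size rather than new entrants, and Table 1 implies only about 10% dilution.

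**The remedy may not recover the effect.** The SAP says outcomes 2-4 are recorded only for those screening positive. If that applies to later visits, excluding entry records leaves a sample selected after treatment. As an assumed illustration, take later scores with means 11 (control) and 8 (treated) and SD 5. Seen only at 10 or above, they average 14.4 and 13.3, so a 3-point effect appears as about 1 point. This stands, and the fix must deal with it.

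**Conclusion.** The point holds for the primary ITT analysis of outcomes 2-4. With the protocol's period effects and quarterly follow-up, the estimate keeps about 90% of the post-entry effect under Table 1's entry schedule, and about 70% under one reading of the Sample Size section combined with enrolment throughout. These figures rest on an entry share the documents do not give, on full scoring of later visits, and on the stated correlations.

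A reader might infer that the bias always runs towards zero. The documents do not support that: with the SAP equations as displayed, dilution is small and the shift from selected entry scores favours the intervention. Prevalence is not affected by this point.

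**What to change.** For outcomes 2-4, amend the SAP to:

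1. treat the entry assessment as each patient's baseline in both control and intervention states;
2. start the outcome series at the next scheduled assessment;
3. include the entry score of the same instrument as a patient-level covariate;
4. keep the protocol's period effects and show them in the SAP equations;
5. analyse later scores for all enrolled patients whether or not they still screen positive, in line with follow-up for the rest of the study;
6. report the all-records model as a sensitivity analysis for the clinic-population reading.

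Three sets of text need reconciling: Table 1 with enrolment over the full trial; the SAP's restriction of outcomes 2-4 to positive screens with cohort follow-up; and that follow-up with the statement in Treatment: IC3D that patients no longer meeting criteria at treatment initiation leave the cohort. Prevalence stays as planned.

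**Cost.** A SAP paragraph, and no new instrument, provided enrolled patients are scored at later visits as the protocol's follow-up implies. There are fewer analysed records: quarter 1 becomes baseline only, and patients first enrolled in the last quarter of months 1-18 contribute no outcome. In the patterns calculated, the minimum detectable effect is still no worse, before any gain from baseline adjustment.

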Daily dose will commence at 20 mg of fluoxetine, or 25 mg of amitriptyline, administered by trained clinical officers.⁴⁹ At monthly follow-up visits, a dose increment or medication change may be considered based on measures of treatment response and side effects, using an Antidepressant Side Effect Checklist—also administered by clinical officers.⁵⁴ This algorithm-based process will be repeated every other week until the patient is fully responding to treatment (PHQ-9 < 5) for a period of three months. Dose escalations of more than one increment and medication changes will be reviewed by a supervising mental health clinician with greater expertise.

Treatment monitoring: Schedule of follow-up visits to monitor side effects and treatment response will vary based on the treatment; for PM+, visits will be weekly for all five sessions, whereas for ADT, the first two visits will be every other week, and then the remainder will be monthly. A Depression Registry will be maintained by a project manager to record treatment data for each visit, which will facilitate future visits, supervision, and fidelity monitoring. Discontinuation will be considered if symptoms are in remission for 9 months.⁵⁵ If on ADT at end of study, it will be sustained as part of usual care.

Training, supervision and fidelity: All counsellors will be trained to implement the depression care model so that related burden is balanced, and to prevent interruptions caused by staff changes. When possible, counsellors will have received prior certification in psychosocial counseling from a local university; however, depending on recruitment success, other counsellors will have no prior mental health training and served in a former capacity as a

community health worker or similar position. Clinical officers responsible for administering ADT will have a degree in clinical medicine (mental health) from a university in Malawi (or equivalent) and will receive additional training on manualized ADT protocols prior to trial initiation.⁵⁶

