There are two main types of approach to dealing with multiple outcomes: multivariate methods and univariate methods. The former method works by jointly modelling all the outcomes at once. However, the joint model of the four outcomes is highly complex, potentially with non-linear sub-models, two-stage models, and shared random effects to allow for correlation (see Appendix), which makes inference difficult or even infeasible without development (and evaluation) of custom software (e.g. a Monte Carlo Maximum Likelihood sampler), which is out of the scope of this project. Instead, we will model the outcomes separately and use a method to correct the family-wise error rate (a univariate methodology).

Statistical model

Aggregate cluster-time outcome

For cluster $j = 1, \dots, J$ at time period $t = 1, \dots, T$ we will screen n_{jt} patients of whom $y_{jt}^{(1)}$ will be diagnosed with depression such that

$$y_{jt}^{(1)} \sim \text{Binomial}(n_{jt}, p_{jt})$$

where we will specify a logistic regression model:

$$\log\left(\frac{p_{jt}}{1-p_{jt}}\right) = z'_{jt}\gamma_1 + \delta_1 D_{jt} + \alpha_{j,1} + \phi_{jt,1}$$

where z_{jt} is a vector of cluster-level covariates, and $\alpha_j \sim N(0, \sigma_\alpha^2)$ and $\phi_{jt} \sim N(0, \sigma_\phi^2)$ are cluster and cluster-time random effects, respectively.

Individual-level outcomes

For patient $i = 1, \dots, N$ who has depression the outcome is $y_{ijt}^{(k)}$ for outcomes $k = 2, 3, 4$. For each outcome we specify the linear model:

$$y_{ijt}^{(k)} = x'_{ijt}\beta_k + z'_{jt}\gamma_k + \delta_k D_{(i)jt} + \theta_{i,k} + \alpha_{j,k} + \phi_{jt,k} + e_{ijt,k}$$

where x_{ijt} is a vector of patient-level covariates $\theta_i \sim N(0, \sigma_\theta^2)$ is an individual-level random effect and e_{ijt} is an independent, identically distributed error term.

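### The minimum detectable effects for PHQ-9 severity, WHODAS and EQ-5D ignore clustering within PM+ therapy groups, so they are optimistic by an amount the documents do not let us fix

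*Protocol*

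**What the plan says.** Under Treatment: IC3D, the Protocol augments usual care with PM+ "through provision of manualized, group-based counseling sessions". PM+ comprises five weekly sessions. It is encouraged on its own below a PHQ-9 of 15 and together with antidepressants at 15 or above, so it is the common element in both severity strata.

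The model in Analysis of Intervention Effects has random effects for patient, clinic and clinic-time: "The models will be at the patient-level, nested within clinic-months and clinics". The SAP model for individual-level outcomes has the same three terms plus a residual that "is an independent, identically distributed error term". No term is specific to the intervention state or to the therapy group.

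The Sample Size section says that power follows from that analysis model, for "a two-sided null value of no effect" and "with a type I error rate of 0.05". Its correlation inputs are an ICC of 0.05, "a cluster autocorrelation coefficient (CAC) of 0.80, and an individual autocorrelation coefficient (IAC) 0.80". It assumes 30 enrollees per facility per three-month step and 15% loss. Neither document gives a PM+ group size, an expected uptake or a group ICC.

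For inference, both documents re-randomise whole clinics. The SAP (Statistical Inference) bases p-values and intervals on studentised generalised residuals. The Protocol does not mention studentising.

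**The concern.** Patients in one PM+ group share sessions, group process and delivery quality. The plan itself expects delivery to matter: under Mediators and Moderators, the Protocol says that fidelity scores predict patient outcomes in depression care, and the SAP addendum measures coverage of PM+ components session by session. Some within-group correlation therefore follows from the trial's own reasoning.

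This correlation exists only once a clinic has switched. A clinic intercept is the same before and after switching, so it cannot represent it. An independent clinic-time effect does not represent a group effect that its members carry into later quarters. A stepped wedge draws much of its information from the before-after contrast within clinics, and the omitted variance enters there.

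Two things are at stake. The first is the precision claimed for outcomes 2-4. The second, more conditionally, is the error rate of any interval that relies on the model's own variance.

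**Working it through.** **Inputs from the Protocol.** 14 clinics in five arms of 2-3, taken as 3, 3, 3, 3, 2. Months 1-18, so six three-month periods. m = 30 × 0.85 = 25.5 patients per clinic-period. ICC 0.05, CAC 0.80, IAC 0.80, two-sided 5%, power 80%.

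**Assumptions, not in the documents.** Group size k = 8 (range 6-10), group ICC ρ = 0.01-0.10 (expressed as a share of the plan's total variance), and uptake u = 100% unless stated.

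**Variance components, total SD = 1.** Clinic 0.05 × 0.80 = 0.04. Clinic-period 0.05 × 0.20 = 0.01. Patient 0.95 × 0.80 = 0.76. Residual 0.95 × 0.20 = 0.19.

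**Plan-input MDE.** The SE of the treatment effect comes from generalised least squares on clinic-period means with period fixed effects, and MDE = (1.960 + 0.842) × SE.
- All patients retained: SE 0.0514, MDE 0.144 SD.
- Complete turnover (IAC set to 0): SE 0.0814, MDE 0.228 SD.

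The Protocol's Table 2 values are not in the text available to this review, so these figures cannot be compared with it.

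**Adding the therapy group.** In treated clinic-periods the mean gains variance v = u × ρ × k / m. At ρ = 0.05 and k = 8, v = 1 × 0.05 × 8 / 25.5 = 0.0157. With retained patients the group effect persists across periods; with turnover it is drawn afresh each period. The estimator keeps the planned model's weights, and power at the plan-input MDE is Φ(MDE / SE_new − 1.960).

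For retained patients at ρ = 0.05, SE_new = 0.0617, which is 20% larger. Power is Φ(0.1441 / 0.0617 − 1.960) = Φ(0.376) = 65%, and the MDE at 80% power becomes 0.173 SD.

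| Group ICC (k = 8, full uptake) | Retained: MDE (SD) | Retained: power | Turnover: MDE (SD) | Turnover: power |
|---|---|---|---|---|
| 0 | 0.144 | 80% | 0.228 | 80% |
| 0.01 | 0.150 | 77% | 0.231 | 79% |
| 0.02 | 0.156 | 73% | 0.235 | 78% |
| 0.05 | 0.173 | 65% | 0.245 | 74% |
| 0.10 | 0.197 | 53% | 0.260 | 69% |

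Over k = 6-10 and ρ = 0.02-0.10, power is 49-75% with retention and 67-78% with turnover. At ρ = 0.05 and k = 8, 60% uptake with full retention gives 70%. An intermediate case, with half the patients retained per step and 50% uptake, has a plan-input MDE of 0.211 SD. At ρ = 0.05 this rises to 0.223 SD, with power of 75.5%.

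Re-weighting for the group variance barely helps: at ρ = 0.05 the MDE is 0.172 instead of 0.173 SD (retained) and 0.244 instead of 0.245 SD (turnover).

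**Error rate at zero mean effect.** This was simulated on clinic means with 999 re-randomisations in 1,500-4,000 runs, at ρ = 0.05, k = 8, with persisting group effects:
- REML Wald test: 7.4%.
- Clinic permutation, unstudentised: 7.5%.
- Clinic permutation, scaled only by the model SE: 6.5-7.8%.
- Clinic permutation, studentised with a between-clinic variance: 4.8%.

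At ρ = 0.10 the Wald and unstudentised tests reach 9.8% and 9.6%, against 5.1% for the robust version (5.9% with groups of 12). When group effects are new each period, all stay near 5%.

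Robust studentisation has a price with 14 clinics. Without any group effect, simulated power at 0.144 SD was 77% unstudentised and 73% with the robust version.

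**Simplifications.** Equal clinic sizes, the 13 restricted allocations ignored, no stepdown adjustment, and a robust score statistic standing in for the SAP's statistic.

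**The case against.** The strongest reply concerns inference. P-values and intervals do not come from model standard errors. Clinics are re-randomised whole, any groups nested in clinics move with them, and the SAP studentises. A reader might infer from the missing term that the intervals are too narrow. The documents do not support that: a robustly studentised test held its level above. They do not exclude it either. The SAP justifies studentising by optimality and equal scale across outcomes, does not say that the variance is between-clinic, and takes its interval method from a reference not yet filled in. Re-randomisation is exact when the intervention affects nobody, but not automatically when group effects merely average to zero.

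A reader might also conclude that the trial lacks 80% power. That cannot be shown. The 80% defines the MDEs, whose values are not visible, and group ICC, group size and uptake are all unstated. The 65% case is demanding: full retention, full uptake and a persisting group effect. The cohort is open, patients choose their treatment, and outcomes 2-4 are recorded only for those who screen positive at the visit. This objection stands as to size, not direction. The IAC of 0.80 takes credit for repeated measures on the same patients, which is where the loss is larger.

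Nor do the documents say that each group is led by one counsellor, so the argument here rests on shared sessions only.

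Finally, one might want the group term in the primary model. That is not justified: re-weighting gains almost nothing, and group membership arises after randomisation.

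**Conclusion.** The point holds as one about stated precision. Neither the power inputs nor the models allow for therapy-group variance in the treated state, so for any positive group correlation the MDEs for outcomes 2-4 are optimistic. At an assumed group ICC of 0.05 with groups of 8 and full uptake, the MDE grows by 20% with full retention (0.144 to 0.173 SD) and by about 7% with full turnover (0.228 to 0.245 SD). At ICC 0.01 the cost is only 1 to 3 power points.

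The effect on error rates is secondary and conditional. At ICC 0.05 there is a mild excess, about 6.5-8% against a nominal 5%, and only if group effects persist and the test or interval relies on the model's own variance or on an unstudentised permutation statistic. The planned randomisation approach is sound if its studentisation is cluster-robust. This should be addressed, but it does not invalidate the design or the primary analysis.

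**What to change.** 1. **Sample Size and Table 2 (Protocol).** State the planned PM+ group size and expected uptake, and restate the MDEs for outcomes 2-4 over a group ICC of 0.02-0.10. Enrolment stays as it is.
2. **Statistical Inference (SAP).** Keep the clinic-level randomisation test as primary. State that the statistic is studentised with a cluster-robust, between-clinic variance, and acknowledge that this costs some power with 14 clinics.
3. **Treatment monitoring (Protocol) and Statistical model (SAP).** The Protocol already provides that "A Depression Registry will be maintained by a project manager to record treatment data for each visit". Add the PM+ group identifier to that record, because it may be hard to recover later. As a sensitivity analysis, report the models for outcomes 2-4 with a random effect for PM+ group, or for clinic-by-treatment, that acts only in the treated state, and give its variance.

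The cost is one registry field, a re-run of the power calculation and one extra model for each of three outcomes. The stated MDEs become somewhat larger.
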